8.2 Outliers

The WHO Growth Standards 2006 (Page 14 in https://www.who.int/childgrowth/software/anthro_pc_manual_v322.pdf) consider the following metrics as biologically implausible and recommend excluding these from analysis of nutritional surveys:

WAZ <-6 or >5 , or LAZ <-6 or >6 , or WLZ <-5 or >5

Data points outside these bounds will be considered missing and excluded from analysis for Primary Objective 2 and Secondary Objective 1, both for the Per Protocol and the Intention to Treat cohorts. It should be noted that trial inclusion/exclusion criteria excluded from enrolment children with WLZ ≤ -3 at baseline.

Participants whose length on day 90 is less than their length on day 1 will have the respective z-scores calculated and will remain included in analysis for Primary outcome 2. This is because there is likely to be bidirectional bias in repeated measurements. Negative deviances in length are likely to occur only rarely, while similar sized positive deviance in length are difficult to distinguish from correctly recorded gains in length over time. Excluding the negative results only would bias the total cohort towards a larger difference from baseline. Keeping them in the cohort is the more conservative option.

9 Statistical analyses

9.1 Primary outcome 1 - 180 day Mortality

We will report the unadjusted risk ratio (RR) of all-cause death by trial allocation arm, which will be the number of deaths over number of persons in each trial allocation arm, and report either a χ^2 -test of $[(\text{death/placebo})/(\text{death/azithromycin})]$ or a Z-test of the $\log[(\text{death/placebo})/(\text{death/azithromycin})]$.

We will examine the 180-day fatality by randomized treatment groups using log-binomial mixed effects models to calculate the risk ratio and 95% confidence bound. Models will include trial site indicators as fixed effects to account for the randomization schema. The primary analysis would only include site as this is the stratified randomization factor. Fatality effect estimates will be presented in Table 2.

Regression model for the outcome of mortality in the ABCD trial will be defined as the following log-binomial mixed effects model:

$$\log Pr(Y_i = 1) = \beta_{0c} + \beta_1 C_i + \beta_2 Z_i \times 1_{\{t>t_0\}} + \varepsilon_i$$

– Model 1

Where

$$Y_i = \begin{cases} 1 & \text{died} \\ 0 & \text{alive at day 180} \end{cases}$$

And

$$\beta_{0c} = \beta_0 + b_c$$

Under this definition we are accounting for clustering at clinic level. The b term is a random effects for the c^{th} clinic, and take account of the variance due to clustering within clinic.

The term $\beta_1 C_i$ is the fixed effect of country, with C_i representing the country of enrolment for child i .

The term $\beta_2 Z_i$ is the fixed effect of azithromycin, with Z_i representing the treatment allocation for child i where

$$Z_i = \begin{cases} 1 & \text{azithromycin} \\ 0 & \text{placebo} \end{cases}$$

The term ε_{ij} is the variance component due to random error for child i at time j .

Now if $\mu_i = \log Pr(Y_i = 1)$ then Y is distributed as

$$Y_i \sim \text{Binomial}(\mu_i | b_c)$$

and Relative Risk of death by $Z_i = \exp(\beta_1)$

Extending Model 1 to admit child level covariates, we have:

$$\log Pr(Y_i = 1) = \beta_{0c} + \beta_1 C_i + \beta_2 Z_i \times 1_{\{t > t_0\}} + \beta_3 X_{ij} + \varepsilon_{ij}$$

- Model 2

Where X_{ij} is the vector of effect-modifying covariates of child i at time j :

$$X_{ij} = \begin{cases} \text{age category } (< 6m, 6 - 11m, \geq 12m) \\ \quad + \text{Sex} \\ \quad + \text{Reason for enrolment} \quad \quad \quad \text{(See Section 4.5)} \\ \quad + \text{Wealth quintile} \end{cases}$$

Where randomization resulted in imbalanced covariates (p-value of t-test or χ^2 test of <0.2 on univariable analysis), sensitivity analysis will include in vector X_{ij} confounders that are imbalanced (e.g. but not limited to: sex, wasting, stunting, dehydration) where X_{ij} is a vector that includes imbalanced covariates of child i at time j (those shown are just exemplary):

$$X_{ij} = \begin{cases} \dots \\ \quad + \text{wasting} \\ \quad + \text{dehydration} \dots \end{cases}$$

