10.1 Primary Objectives

1. *To compare rates of all-cause mortality in the 180 days following enrolment for an episode of high risk diarrhoea without dysentery among children 2 to 23 months of age living in low resource settings who are randomized to receive a 3-day course of azithromycin or placebo.*

Period prevalence of death will be compared between randomly-assigned treatment groups using relative risk regression. Mortality will be defined as a binary variable and will be defined as any event of death from time of randomization to end of day 180. Time to death will not be considered. Censored individuals will be retained in the denominator. For the primary ITT analysis, the following model will be used:

$$E(Y|\text{randomisation arm}) = e^{(\beta_0 + \beta_1 X_{azm})}$$

where x_{azm} is an indicator variable specifying randomized to the azithromycin group ($x_{azm}=1$) or not ($x_{azm}=0$). The risk ratio comparing the risk of death in children randomized to azithromycin vs. placebo will be determined by e^β . The statistical significance of this comparison will be determined by Wald test.

If the baseline assessment of randomization reveals an imbalance in characteristics between the randomization arms, we will evaluate these characteristics as potential confounders in a sub-analysis secondary to the ITT. The following baseline characteristics will be evaluated for balance between randomization arms (median age, stunting prevalence, wasting prevalence, prevalence of “some” and “severe” dehydration, site [Bangladesh, India, Kenya, Malawi, Mali, Pakistan, Tanzania], hospital admission, and median duration of diarrhoea). Potential baseline confounders will be added stepwise in the relative risk model with randomization arm as follows:

$$e^{(\beta_0 + \beta_1 X_{azm} + \beta_i X_i)}$$

Where i are the baseline characteristic(s) included in the model. These will be maintained in the model if their inclusion in the model changes the hazard ratio by more than 10%. Also, in a sub-

analysis, separate analysis for each site (Bangladesh, India Kenya, Malawi, Mali, Pakistan, Tanzania) will be presented to describe differences in treatment effects between sites (no formal hypothesis tests within each site stratum will be performed).

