4.4 Sensitivity analyses examining potential baseline imbalances

We will report baseline characteristics of participants by trial allocation arm (Table 1), we will examine imbalance by trial arm, accepting that these arose by random chance, and will not conduct hypothesis tests for difference by allocation arm. However we will include any apparent imbalances in sensitivity analyses for all primary and secondary outcomes. In sensitivity analyses, we will include as model covariates characteristics which on univariable analysis are associated with the outcome of interest with a p-value <0.10 . If the point-estimates for the unadjusted and adjusted analyses of the primary outcomes differ by more than 10%, the adjusted analysis will be presented as primary.

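### SAP 9.1 reads the treatment relative risk from the country coefficient, and writes the unadjusted risk ratio as placebo over azithromycin, the reverse of its own model and of the protocol

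*SAP*

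**What the plan says.** **Coefficients.** SAP 9.1 defines Model 1 with two fixed effects. "The term $\beta_1 C_i$ is the fixed effect of country", and "The term $\beta_2 Z_i$ is the fixed effect of azithromycin", where Z = 1 is azithromycin and Z = 0 is placebo. A few lines later, the line that begins "and Relative Risk of death by" sets the relative risk by Z equal to exp(β1).

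**Unadjusted ratio.** The opening sentence of SAP 9.1 describes the crude risk ratio as "number of deaths over number of persons in each trial allocation arm". It then offers a chi-square test of a ratio or a Z-test of its logarithm. In both, the ratio is (death/placebo)/(death/azithromycin). No other arm-to-arm ratio is written out in the section.

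**Protocol.** Section 10.1 defines the estimate as "The risk ratio comparing the risk of death in children randomized to azithromycin vs. placebo". Its model has no country term, so there β1 is the treatment coefficient. Section 10.3 sizes the trial on a relative risk of 0.65 in the intervention group, which is the same direction.

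**Tables.** SAP Tables 2 and 4 each have one RR column, footnoted as coming from the adjusted mixed model. Neither states which arm is the numerator.

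**The concern.** These lines tell the analyst what number to report for a primary endpoint. The only line in SAP 9.1 that links a coefficient to the relative risk names the wrong one, and the only crude ratio written out points the wrong way. Nothing in the table shells corrects either.

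Taken at face value, the plan either has no valid definition of the model-based relative risk, or labels a contrast between countries as a treatment effect. It would also present a crude ratio above 1 for a benefit. SAP section 11 treats the statistician's analyses as final and rules out parallel analyses of the same question, so the written formulas ought to be right.

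**Working it through.** **1. Direction of the design figure.** Inputs from Protocol 10.3: control mortality 2.7%, relative risk 0.65, 90% power, two-sided alpha 0.05, 10% loss, inflation factor 1.009.

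- Azithromycin risk = 0.027 × 0.65 = 0.01755.
- Standard two-proportion formula, no continuity correction: n = [1.960 √(2p̄q̄) + 1.282 √(p₁q₁ + p₂q₂)]² / (p₁ − p₂)², with p̄ = 0.022275. This gives 5,123 per arm.
- 5,123 / 0.90 = 5,693 (plan: 5,696). 5,693 × 1.009 = 5,744 (plan: 5,750).

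The plan's sample size is reproduced closely, with 0.65 taken as azithromycin over placebo.

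**2. The crude ratio in each direction.** Expected deaths among 5,750 per arm, rounded: placebo 5,750 × 0.027 = 155; azithromycin 5,750 × 0.01755 = 101.

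- SE of log RR = √(1/101 − 1/5,750 + 1/155 − 1/5,750) = 0.1265.
- Azithromycin over placebo: 101/155 = 0.65; 95% CI 0.51 to 0.83; z = −3.386.
- Placebo over azithromycin, as written: 155/101 = 1.53; 95% CI 1.20 to 1.97; z = +3.386.
- Two-sided p = 0.0007 both ways.

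The exact reciprocal of 0.65 is 1.54; 1.53 comes from rounding deaths to whole numbers. Only the sign of z changes, so the test is the same and the reported estimate and interval are inverted.

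**3. What exp(β1) would be.** Under the SAP's definitions β1 belongs to country. With seven countries that factor has six contrasts, so there is no single exp(β1). As an illustration, assume that baseline risks equal the five case-fatality figures for trial countries in Protocol 13.5, Table 1 (Kenya 3.5%, Pakistan 1.3%, Mali 1.1%, Bangladesh 0.50%, India 0.13%), with Bangladesh as reference and a true treatment RR of 0.65. A log-binomial fit to the expected counts returns:

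- Country terms: 3.5/0.50 = 7.0; 1.3/0.50 = 2.6; 1.1/0.50 = 2.2; 0.13/0.50 = 0.26.
- exp(β2) = 0.65.

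The country terms are neither the treatment relative risk nor its reciprocal. The model itself recovers 0.65 from β2.

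**The case against.** The strongest reply is that these are notation slips that a competent analyst would read through. Model 1 codes azithromycin as 1 and names β2 as its effect, so the fitted model gives azithromycin versus placebo. The relative-risk line says that it is the risk by Z, so the intent is clear, and a seven-level factor cannot yield one number to misreport. Since β1 is the treatment coefficient in Protocol 10.1, carried-over notation is a plausible cause. The sentence describing the crude ratio gives no direction, and the reversed ratio appears only as the argument of a test that inversion does not change. All of this stands and limits the consequence. It does not make either formula correct.

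A reader might go further and infer three things that the documents do not support.

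- *That the primary model estimate is inverted.* It is not. SAP 9.1 makes the site-adjusted model primary, and its coding agrees with the protocol.
- *That Table 2 would print two conflicting relative risks.* Table 2 has a single RR column, taken from the mixed model, and shows n/N by arm beside it.
- *That the switching rule in SAP 4.4 would be triggered.* That rule applies if the unadjusted and adjusted point estimates "differ by more than 10%, the adjusted analysis will be presented as primary". Its paragraph concerns sensitivity models that add baseline covariates, so the natural comparison is the model without and with those covariates. Both have azithromycin coded 1, and inversion cannot affect them. The other reading is not excluded: SAP 9.1 uses the word unadjusted for the crude ratio, and the Table 2 footnote calls the mixed model adjusted. If 4.4 were read as comparing those two, with the crude ratio left as the reciprocal of the model RR, the difference relative to the model RR would be 1/RR² − 1. That is 137% at 0.65, and it exceeds 10% whenever RR is below 0.953 or above 1.054. So the rule could trip on that reading; the text does not show that it would.

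**Conclusion.** Both errors are on the face of SAP 9.1 and should be corrected, because they concern the reported effect for a primary endpoint. The relative risk for treatment is attributed to the country coefficient, contrary to the section's own definitions. The crude ratio as written runs opposite to Model 1, Protocol 10.1 and the design value, so that 0.65 would read as 1.54.

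The reach is narrow. The fitted model, the two-sided p-value and the sample size are unaffected. What is affected is the coefficient named as the relative risk, and the direction of the crude ratio and its confidence interval. The direction point needs only the formulas as printed. The intervals quoted assume the protocol's design rates with all 5,750 children per arm analysed. The country contrasts are illustrative only.

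**What to change.** In SAP 9.1:

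- change exp(β1) to exp(β2) in the relative-risk line;
- write the unadjusted risk ratio as (deaths/N azithromycin)/(deaths/N placebo), and use the same ratio in the test statistic.

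In SAP Tables 2 and 4, label the RR column as azithromycin versus placebo. It would also help to add a clause to SAP 4.4 naming the two models whose estimates are compared, which closes the alternative reading.

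The cost is a few lines of text, best issued as a dated correction before the intervention code is broken. No data collection, model or sample size changes.

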9.2 Primary outcome 2 - Change in Length-for-age z-score

The group means at baseline and endline and the mean ΔLFAZ will be presented by treatment group in Table 3. We will use generalized linear mixed models with ΔLAZ as the response variable and treatment group, fixed effects for study site and variable effects for child (which accounts for baseline LAZ) and clinic as the explanatory variables.

The primary analysis for this variable will only include the site since this is the stratified randomization..

Regression model for the outcome change from baseline in length for age Z-score (Δ LFAZ) in the ABCD trial is defined as the following linear mixed-effects model:

$$Y_{ij} = \beta_{0_{c_i}} + \beta_1 C_i + \beta_2 Z_i \times 1_{\{j=1\}} + \varepsilon_{ij} \quad \text{- Model 3}$$

Y_{ij} is Δ LFAZ in child i at time j , where

$$j = \begin{cases} 1 & \text{day 90} \\ 0 & \text{enrollment} \end{cases}$$

$\beta_{0_{c_i}}$ is the random effect of child i at clinic c , where

$$\beta_{0_{c_i}} = \beta_0 + b_{c_i} + b_{0_i}$$

Under this definition we are accounting for clustering at clinic level and at child level. The b terms are random effects for the c^{th} clinic and the i^{th} child, and take account of the variance due to clustering within clinic or over time in a given child. The latter is effectively also an adjustment for baseline LFAZ and WFAZ for that child. Should these models not converge, we will allow clinic to remain the random effect, but adjust for baseline LFAZ as a fixed effect.

The term $\beta_1 C_i$ is the fixed effect of country, with C_i representing the country of enrolment for child i .

The term $\beta_2 Z_i$ is the fixed effect of azithromycin, with Z_i representing the treatment allocation for child i where

$$Z_i = \begin{cases} 1 & \text{azithromycin} \\ 0 & \text{placebo} \end{cases}$$

The term ε_{ij} is the variance component due to random error for child i at time j .

Participants whose Day 90 visit occurred outside the protocol defined window will be included in the Intention to Treat Analysis. Sensitivity analysis will take account of the time varying nature of this visit by fitting a model that allows the effect of azithromycin to vary as a function of time is:

$$Y_{ij} = \beta_{0_{c_i}} + \beta_1 C_i + \beta_2 Z_i \times 1_{\{t>t_0\}} + \beta_3 Z_i t_{ij} \times 1_{\{t>t_0\}} + \varepsilon_{ij}$$

- Model 4

Model 4 allows for a proportional effect of fixed magnitude (parameter β_2) *and* for a time-varying effect (parameter β_3).

Under Model 2 the term $\beta_{0_{ci}}$ is the random effect of child i at clinic c , as it was above, but where

$$\beta_{0_{ci}} = \beta_0 + b_{ci} + b_{0i} + b_{1i}t_{ij}$$

As before, should these models fail to converge, we will allow clinic to remain the random effect, but adjust for baseline LFAZ as a fixed effect.

Extending Model 4 to admit child level covariates, we have:

$$Y_{ij} = \beta_{0_{ci}} + \beta_1 C_i + \beta_2 Z_i \times 1_{\{t > t_0\}} + \beta_3 Z_i t_{ij} \times 1_{\{t > t_0\}} + \beta_4 \mathbf{X}_{ij} + \varepsilon_{ij}$$

- Model 5

Where \mathbf{X}_{ij} is the vector of effect-modifying covariates of child i at time j :

$$\mathbf{X}_{ij} = \begin{cases} \text{age category } (< 6m, 6 - 11m, \geq 12m) \\ \quad + \text{Sex} \\ \quad + \text{Wealth quintile} \end{cases}$$

Where randomization resulted in imbalanced covariates, sensitivity analysis will include in vector \mathbf{X}_{ij} confounders that are imbalanced (e.g. but not limited to: sex, wasting, stunting, dehydration) as previously described.

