In a per-protocol analysis, also secondary to the ITT analysis, relative risk regression will be fit as described above among the subset of children with documented completion of the full course of treatment (direct observation of 3 daily doses and) with at-risk-time beginning on date of observed third dose.

2. *To compare changes in linear growth (Δ LAZ) in the 90 days following enrolment for an episode of high risk diarrhoea without dysentery among children 2 to 23 months of age living in low resource settings who are randomized to receive a 3-day course of azithromycin or placebo.*

Analysis strategy: Linear regression model will be used to compare mean Δ LAZ across the treatment groups in surviving children. Δ LAZ will be operationalized as the difference in LAZ between the 90-day follow-up visit and LAZ at baseline. For the primary ITT analysis, the following model will be used:

$$E(Y|\text{randomisation arm}) = \beta_0 + \beta X_{azm}$$

where Y =mean Δ LAZ, and x_{azm} is an indicator variable of being randomized to the azithromycin group ($x_{azm}=1$) or not ($x_{azm}=0$). The mean difference in Δ LAZ in children randomized to azithromycin vs. placebo will be determined by (β). The statistical significance of this comparison will be determined by independent t-test.

If the baseline assessment of randomization reveals an imbalance in characteristics between the randomization arms, we will evaluate these characteristics as potential confounders in a sub-analysis secondary to the ITT as described in the mortality time to event analyses. Potential baseline confounders will be added stepwise in the linear regression model with randomization arms and maintained in the model if inclusion in the model changes the effect estimates (difference in means) by more than 10%.

In a per-protocol analysis, also secondary to the ITT analysis, a linear regression model will be fit as described above among the subset of children with documented completion of the full course of treatment (direct observation of 3 daily doses).

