Mortality among young children with acute watery diarrhea who additionally have dehydration or malnutrition is high in low-income countries. Linear growth faltering is another important consequence of diarrhea, with potentially long-term effects on school performance, cognitive development and earning potential. Multi-country evidence shows that bacterial pathogens contribute substantially to mortality and linear growth faltering and with the widespread introduction of rotavirus vaccine, these bacteria will likely make a proportionally greater contribution to childhood diarrhea.

The ABCD Trial (AntiBiotic treatment of moderate to severe Childhood Diarrhea to reduce diarrhea-related mortality and stunting in children: multi-country randomized double-blinded placebo-controlled trial) is a WHO-sponsored 7-country double-blind randomized placebo-controlled 2-arm trial of a directly observed 3-day course of azithromycin vs placebo, powered for detection of 35% relative reduction in mortality and a 0.04 increase in length for age Z-score among children with medically-attended moderate to severe gastroenteritis. The trial will recruit in total 11,500 children (5,750 per treatment arm), in Bangladesh, Pakistan, India, Malawi, Tanzania, Kenya and Mali. Randomization was conducted using permuted blocks stratified by country.

This document outlines the plans for the statistical analysis of the primary and secondary objectives of the trial.

DSMB meeting and update of the SAP: This document was updated in Aug 2019 after the DSMB took a decision in their June 2019 meeting to halt recruitments into the ABCD trial because of (a) very small numbers of deaths (the primary outcome) and the strong likelihood of futility (b) a statistically significant but clinically less relevant difference in LAZ scores between the groups.

While the DSMB received information on allocations, the study teams, WHO coordinators and data management group (RTI) remained blind to the allocation until receipt of the DSMB report of 27th June 2019 which recommended that further recruitment be stopped. Sites were notified by Trial Sponsor on July 1, and all sites ceased recruiting in subsequent days, with last participants recruited on July 10.

3 Study objectives

3.1 Primary Objectives:

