4.6 Adjusting for baseline measure in change from baseline outcomes

Primary Objective 2 is change from baseline in length-for-age Z-score. Change from baseline outcomes will be adjusted for the baseline value in order to avoid the phenomenon of regression to the mean. In an analysis of covariance (ANCOVA) framework, this can be achieved by including baseline metric in the model. Identically, the same adjustment is achieved by including participant level covariates as random effects in a mixed effects model. This accounts for the clustering of length-for-age and weight-for-length across the two timepoints (enrolment and day 90) within each enrolled participant.

5 Hypotheses to be tested

Primary Objective 1 – 180 day mortality:

Null hypothesis: Among children 2-23 months of age with moderate to severe diarrhea, 180 day mortality is independent of treatment allocation to placebo or to a 3-day course of oral azithromycin.

Alternative hypothesis: Among children 2-23 months of age with moderate to severe diarrhea, 180 day mortality is not independent of exposure i.e. those allocated to receive a 3-day course of oral azithromycin compared to those allocated to receive oral placebo..

Primary Objective 2 – Change in Length-for-age z-score:

Null hypothesis: Among children 2-23 months of age with moderate to severe diarrhea, the mean change from baseline in length-for-age z-score (ΔLAZ) over the 90 day follow-up period is independent of treatment allocation to placebo or to a 3-day course of oral azithromycin.

Alternative hypothesis: Among children 2-23 months of age with moderate to severe diarrhea, the mean change from baseline in ΔLAZ over the 90 day follow-up period is not independent of exposure i.e. among those treated with a 3-day course of oral azithromycin than those treated with a placebo preparation.

Secondary objective 1 – Hospitalization by day 90

Null hypothesis: Among children 2 to 23 months of age with moderate to severe diarrhea, the proportion of children hospitalized by day 90 after enrolment, is independent of treatment allocation to placebo or to a 3-day course of oral azithromycin.

Alternative hypothesis: Among children 2 to 23 months of age with moderate to severe diarrhea, the proportion of children hospitalized by day 90 after enrolment, is not equal in the placebo arm and the arm receiving 3-day course of oral azithromycin.

Secondary objective 2 – Hospitalization or death by day 90

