9.4.1 Outcome Definitions

1. Δ WLZ = WLZ at endline visit *minus* WLZ at randomization visit
2. Δ WAZ = WAZ at endline visit *minus* WAZ at randomization visit
3. Δ MUAC = MUAC at endline day visit *minus* MUAC at randomization visit

In sensitivity analysis the endline visit date will be restricted to those who had the visit from study day 91 to 100.

The group means for WLZ, WAZ and MUAC at baseline, endline and mean change will be presented by group as indicated in Table 3. We will use generalized linear mixed models with Δ WLZ, Δ WAZ or Δ MUAC as response variables and treatment group and fixed effects for study country and random effects for clinic and child as the explanatory variables. A sensitivity analyses including potential effect modifiers and unbalanced confounders will be done. Modeling will be analogous to Models 3-5 listed in Section 9.2, but where Y_{ij} is Δ WLZ, Δ WAZ or Δ MUAC respectively, in child i at time j .

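### The primary ΔLAZ model (SAP Model 3) has no day-90 main effect and relies on a child random intercept for baseline adjustment; under no reading does it do what the SAP says

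*SAP*

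**What the plan says.** SAP 9.2 makes ΔLAZ the response and lists treatment, then "fixed effects for study site and variable effects for child (which accounts for baseline LAZ) and clinic as the explanatory variables". Model 3 indexes the response by child and time, with j = 0 at enrolment and j = 1 at day 90. Its fixed terms are an intercept, country, and treatment multiplied by an indicator for j = 1. No term lets the mean differ between enrolment and day 90 in the placebo arm.

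SAP 4.6 requires change outcomes to be adjusted for baseline, names ANCOVA, and then claims: "Identically, the same adjustment is achieved by including participant level covariates as random effects in a mixed effects model". Baseline LAZ becomes a covariate only conditionally: "Should these models not converge, we will allow clinic to remain the random effect, but adjust for baseline LFAZ as a fixed effect".

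The row layout is left open.

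- Pointing to two rows: the j index; SAP 4.6, which speaks of "clustering of length-for-age and weight-for-length across the two timepoints (enrolment and day 90) within each enrolled participant"; and SAP 9.2, where the random effects "take account of the variance due to clustering within clinic or over time in a given child".
- Pointing to one row: ΔLAZ as the named response, and Protocol 10.1, where ΔLAZ is "operationalized as the difference in LAZ between the 90-day follow-up visit and LAZ at baseline".

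Models 4 and 5 also lack a fixed common time effect. SAP 9.4.1 extends the structure to ΔWLZ, ΔWAZ and ΔMUAC: "Modeling will be analogous to Models 3-5 listed in Section 9.2".

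**The concern.** In a stacked model without a time main effect, the treatment-by-day-90 term is the only fixed term that can represent movement between visits. If mean LAZ shifts in both arms, that term picks up part of the shift and reports it as a drug effect. In a one-row model, a random intercept with one observation per child cannot be told apart from the residual, so it adjusts for nothing.

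This is one of two primary outcomes and the planned effect is small, so a modest common shift could create, hide or reverse the result. Timing matters too. SAP section 2 records that the DSMB had already seen "a statistically significant but clinically less relevant difference in LAZ scores between the groups", and SAP 6.4 allows the plan to be amended after a run by blinded group. A primary model open to several readings should be settled before that run.

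**Working it through.** **Inputs.** From Protocol 10.3: target difference 0.04, SD of change s = 0.6 or 0.7, 5,750 per arm, 10% loss. Evaluable n = 5,750 × 0.9 = 5,175 per arm. Recruitment stopped early and the achieved number is not given, so 3,500 per arm is also shown as an assumption. Also assumed: LAZ SD σ = 1.0 to 1.5, equal at both visits. Let τ be the true arm effect and δ the mean change common to both arms. The documents do not give δ, so it is varied.

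**Reproducing the plan's figure.** Table 1 gives 4,730 per group for 0.04, SD 0.6 and 90% power. The formula gives 2(1.96 + 1.2816)² × 0.36 / 0.0016 = 4,728.3, rounded up to 4,729. The sample size is not in question.

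**(a) Two LAZ rows per child.** The within-child correlation is ρ = 1 − s²/(2σ²). Generalised least squares with a random intercept and no time effect gives

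- E(β2) = τ + kδ, with k = 2(1 + ρ)/(3 + ρ)
- Var(β2) = σ²(1 − ρ²) × 4/(3 + ρ) / n

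The extremes of k are:

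- σ = 1.0, s = 0.7: ρ = 1 − 0.49/2 = 0.755; k = 3.51/3.755 = 0.935.
- σ = 1.5, s = 0.6: ρ = 1 − 0.36/4.5 = 0.92; k = 3.84/3.92 = 0.980.

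Type I error (τ = 0) across the grid:

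| n per arm | SE of β2 | \|δ\| for 10% rejection | \|δ\| for 50% rejection |
|---|---|---|---|
| 5,175 | 0.0081–0.0096 | 0.0055–0.0066 | 0.0165–0.020 |
| 3,500 | 0.0099–0.0117 | 0.0067–0.0080 | 0.020–0.024 |

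At an assumed δ = −0.05 the bias is about −0.048 and a true null is rejected in over 98% of trials at either n. With τ = +0.04 and δ = −0.05, the mean of β2 is about 0.040 − 0.048 = −0.008: the sign reverses.

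**(b) Two ΔLAZ rows per child, with enrolment zero by definition.** The child variance is estimated at zero, so the fit reduces to least squares. The intercept averages three cells with means 0, 0 and δ, which gives δ/3. Hence E(β2) = τ + δ − δ/3 = τ + (2/3)δ.

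- True variance: s²/n + s²/(9n) = (10/9)s²/n.
- Model variance at δ = 0: (s²/2)(4/3)/n = (2/3)s²/n, because half the rows are constants.
- SE ratio: √0.6 = 0.775. Rejection under the null: P(|N(0,1)| > 1.96 × 0.775) = 12.9%.
- At 5,175 per arm, type I error is 42–50% at |δ| = 0.02 and 96–99% at |δ| = 0.05.
- With τ = +0.04 and δ = −0.05: 0.04 − 0.0333 = +0.0067.

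**(c) One ΔLAZ row per child.** There is no bias. A test fit of the mixed model to one simulated dataset returned exactly the unadjusted difference (0.0146), while ANCOVA gave 0.0114. With equal LAZ variance at both visits, ANCOVA multiplies the variance by (1 + ρ)/2. Power for 0.04 at 5,175 per arm:

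| SD of change | Unadjusted | ANCOVA |
|---|---|---|
| 0.7 | 82.8% | 84.8–87.4% |
| 0.6 | 92.4% | 93.3–94.5% |

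**The fallback.** It does not state one row per child. Fitted to stacked ΔLAZ rows (1,500 simulated trials), it gave 13.1% rejection at δ = 0, and a mean β2 of −0.033 with 96.0% rejection at δ = −0.05. One-row ANCOVA held 4.7–5.3% throughout.

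**Model 4 on stacked LAZ rows.** The random slope has mean zero and cannot absorb a common shift. With visit times uniform on days 80–100, σ = 1.2, s = 0.7, and 0 to 60% of the change variance in the slope, the day-90 arm contrast is τ + 0.956 to 0.993 × δ.

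**With the correction.** In simulations with s = 0.6 and δ from 0 to −0.20, stacked LAZ with a day-90 main effect and one-row ANCOVA both averaged about 0.000 when τ = 0 and about 0.040 when τ = 0.04, with rejection near 5% under the null.

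**The case against.** The best defence is that one row per child is the natural reading. SAP 9.2 repeatedly names the change as the response, Protocol 10.1 defines it as a single difference, and SAP 8.1 drops children whose change cannot be computed. The time indicator looks like template notation: Models 1 and 6, which are plainly one-row binary models, carry a similar one. On that reading Model 3 reduces to the protocol's unadjusted comparison plus country and clinic. SAP 4.4 also gives some protection against chance imbalance. The power gain lost may be smaller than shown: with a change-on-baseline slope of −0.1 instead of equal variances, it is 0.7 to 1.7 points. Two ΔLAZ rows would require an analyst to enter structural zeros, which is unlikely.

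Much of this stands. One row is the likelier reading, its harm is modest, and the largest error rates depend on an unknown δ or an unlikely layout. It does not rescue the text. The two-timepoint language in 4.6 and 9.2 is real, the equivalence claimed in 4.6 fails for one row, and the fallback may never be triggered: one-row and stacked-ΔLAZ test fits produced warnings yet were still reported as converged. SAP section 11 also rules out parallel analyses, so no second analysis is planned that would expose the problem.

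**Conclusion.** The concern holds. None of the three layouts delivers the baseline-adjusted comparison that SAP 4.6 promises.

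- Two LAZ rows: the primary test is valid only if the common change is close to zero.
- Two ΔLAZ rows: it is invalid even then, with about 13% type I error.
- One row: the estimate is unbiased, but the adjustment is lost, at a cost of about 1 to 4.5 points of power under equal variances.

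The bias multipliers rest on assumed LAZ SDs of 1.0 to 1.5 and vary little over that range. The size of the bias rests on δ, which is unknown. The LAZ losses cited in Protocol 10.3 (0.04 in infants, 0.10 in toddlers) are relative to controls and are not estimates of δ. Because the model as written allows materially different estimates from the same data on a primary outcome, it must be corrected and not left to the analyst.

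**What to change.** Before the code is broken, and before the blinded-group run in SAP 6.4, replace Model 3 with the SAP's own fallback, made unconditional and with one row per child:

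ΔLAZ_i = β0 + β1·(baseline LAZ_i) + country fixed effects + β2·Z_i + clinic random intercept + ε_i

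Use the matching form, each with its own baseline value, for ΔWLZ, ΔWAZ and ΔMUAC. If a two-row model is preferred, make LAZ (not ΔLAZ) the response, add a day-90 main effect to Model 3, and add a fixed effect of time to Models 4 and 5. Amend the equivalence sentence in SAP 4.6 to say that the random-effects form approximates ANCOVA only when a time main effect is included.

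The cost is SAP wording and one line of model code; no new data are needed and the sample size is unaffected.
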